1.5. Optimisation of age-specific sample allocation

To identify the best way to distribute 3,000 samples across age groups, we tested a wide range of candidate allocations. Each allocation defined the proportion of samples assigned to seven age groups (1-2, 2-6, 6-12, 12-19, 19-31, 31-40,and 40-65 years), using proportions that varied by steps of 5% and always summed to 100%.

For each candidate allocation, we simulated 500 synthetic datasets, assigned serostatus based on the predicted seroprevalence by age, and fitted a generalized additive model (GAM) to estimate the overall seroprevalence. We then computed the precision of each scenario as half the width of the 95% confidence interval across simulations. The allocation that achieved the best precision was selected for each pathogen and region.

2. Results

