For measles, the most recent national serological survey was conducted in 2013. To evaluate the sample size needed to estimate the current seroprevalence by age, we use a cohort-based modelling approach to project immunity levels to 2025. This model incorporates historical vaccination coverage, age of vaccination and waning immunity, following methods described by Hens et al. (2015) and Abrams et al. (2014) (30,31). The aim was to obtain both overall and agegroup-specific seroprevalence estimates with a precision of +-2% (width of confidence interval max. 4%). To ensure sufficient sample size of the serumbank for pathogens other than measles, these calculations were repeated for 2 additional pathogens. The additional pathogens (CMV and Hepatitis B) were selected based on their seroprevalence patterns in the population who differ importantly from the measles seroprevalence patterns.

Appendix 5 contains the full methodology and results. With a total sample size of 3,900 samples, precision of overall national seroprevalence estimates for all 3 pathogens would be <2% (and even <1% for measles and Hepatitis B). Not all agegroup-specific estimates would have <2% precision, but all are within acceptable ranges (all <3% precision for measles). To obtain equal precision in the region-specific estimates, similar absolute number of samples would need to be collected from Flanders, Walllonia and Brussels. However, as both the population size as well as

the number of labs in Brussels is much smaller than in Flanders, this is deemed unfeasible. We therefore plan a pragmatic approach and adjust the regional allocation to reflect practical constraints and the actual number of participating laboratories, accepting wider confidence intervals in Brussels. The final distribution of samples by agegroup is then presented in Table 1.

Table 1. Samples distribution - National

Age groups	Number of samples - National
1-4yo	450
5-9yo	450
10–14yo	300
15-19yo	450
19-31yo	450
31-40yo	750
40-65yo	1050
Total	3900

Sample collection and analysis

Sample collection and transport

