1.4. Simulation framework for sample allocation and precision

To assess the precision obtained under different age-based sampling structures, we simulated synthetic datasets by drawing binomial outcomes from the projected age-specific seroprevalence profile (Section 1.2). For each individual in the simulated sample, seropositivity status was assigned using a Bernoulli distribution with probability equal to the predicted seroprevalence at their age. This process was repeated independently 500 times for each sampling scenario. The resulting datasets were used to estimate the seroprevalence in each of the eight predefined age groups. Following the approach described by Blaizot et al. (2019) [1], precision was defined as half of the width of the 95% simulation-based confidence interval across the 500 replicates (simulation runs), calculated for each age group and overall. This framework enabled direct comparison of the expected estimation precision under each sampling design.

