To ensure sufficient precision for all pathogens, we selected the maximum number of samples per age group across the three pathogens as the final recommendation. This results in a total of 3,900 samples nationally, which we divide equally across the three regions, yielding 1,300 samples per region.

Table 4 reports the expected precision of the overall seroprevalence estimates under this allocation. At the national level (3,900 samples per pathogen), the expected precision is 0.82% for measles, 0.85% for hepatitis B, and 1.69% for CMV. At the regional level (1,300 samples per region), expected precision decreases slightly to 1.69% for measles, 1.45% for hepatitis B, and 2.64% for CMV, still within acceptable bounds.

Age group	Measles	НерВ	CMV
1-4yo	5%	5%	15%
5-9yo	15%	15%	5%
10-14yo	5%	10%	10%
15-19yo	15%	5%	10%
19-31yo	15%	10%	10%
31-40yo	20%	25%	15%
40-65yo	25%	30%	35%
Precision	0,88%	0,74%	1,52%

Table 2. Optimal proportion of samples per age group for measles, hepatitis B, and CMV based on national-level simulations.

	Measles	НерВ	CMV	National	Regional
1-4yo	150	150	450	450	150
5-9yo	450	450	150	450	150
10-14yo	150	300	300	300	100
15-19yo	450	150	300	450	150
19-31yo	450	300	300	450	150
31-40yo	600	750	450	750	250
40-65yo	750	900	1050	1050	350
Total	3000	3000	3000	3900	1300

Table 3. Absolute number of samples per age group, assuming 3,000 samples per pathogen. The final allocation (bold values) corresponds to the highest required count across pathogens, resulting in a total of 3,900 samples nationally (or approximately 1,300 per region).

	Measles	НерВ	CMV
National	0,82%	0,85%	1,69%
Regional	1,69%	1,45%	2,64%

Table 4. Expected precision (half-width of the 95% simulation-based confidence interval) for overall seroprevalence estimates under the final allocation. National precision is based on 3,900 samples; regional precision is based on 1,300 samples per region.

Precision by age - national allocation

_	.=			
Age group	Allocation	Measles	НерВ	CMV
1-4yo	450	2,25%	0,50%	4,23%
5-9yo	450	2,61%	0,53%	3,25%
10-14yo	300	1,76%	0,63%	3,50%
15-19yo	450	1,95%	0,73%	3,14%
19-31yo	450	2,88%	1,20%	2,94%
31-40yo	750	2,40%	1,51%	2,78%
40-65vo	1050	1,25%	1.42%	3.02%

Table 5. Expected precision (half-width of the 95% simulation-based confidence interval) for prevalence estimates of each age group under the final allocation.

4. References of Appendix 5

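### The four youngest age bands named in the optimisation text differ from those in the allocation tables, so the quotas cannot be traced to the search described, and the printed bands are not mutually exclusive

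*Protocol*

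**What the plan says.** Appendix 5, section 1.5 sets out the search. Its aim is given as "To identify the best way to distribute 3,000 samples across age groups", over "seven age groups (1-2, 2-6, 6-12, 12-19, 19-31, 31-40,and 40-65 years", "using proportions that varied by steps of 5% and always summed to 100" percent. The winner is chosen on the precision of overall seroprevalence: "The allocation that achieved the best precision was selected for each pathogen and region".

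Appendix 5, section 3 reports the result in its Table 2, captioned "Optimal proportion of samples per age group for measles, hepatitis B, and CMV based on national-level simulations". The rows of that table are 1-4, 5-9, 10-14, 15-19, 19-31, 31-40 and 40-65. Table 3 turns the percentages into counts, and Table 5 gives precision by age; both use the same rows. The final count in each row is the largest of the three pathogen-specific counts.

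The Sample size section of the main protocol carries those counts forward: "The final distribution of samples by agegroup is then presented in Table 1". (That is the protocol's own Table 1; Appendix 5 has a different Table 1, on vaccination coverage.)

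Appendix 5, section 1.4, on the precision simulations, refers to a different number of groups: "estimate the seroprevalence in each of the eight predefined age groups".

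**The concern.** Both lists have seven bands and the three oldest are identical, but the four youngest differ. A percentage found for age 1 alone is not a percentage for ages 1 to 4. No step re-bins one list into the other, so at least one of the two statements behind the recruitment quota must be wrong.

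Table 1 is the only age distribution the protocol gives for filling the serum bank. The discrepancy lies entirely in children and adolescents, an age range in which the study looks for measles vaccination gaps.

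The labels raise a second, separate problem. Strata used to set quotas should place each age in exactly one band. Tubes and labels carry an age code, so the bands need to be settled before materials go out.

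**Working it through.** **1. Reproduce the plan's figures.** Each column of Appendix 5 Table 2 sums to 100%. Multiplying by 3,000, in row order:

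- Measles 5/15/5/15/15/20/25% gives 150/450/150/450/450/600/750.
- Hepatitis B 5/15/10/5/10/25/30% gives 150/450/300/150/300/750/900.
- CMV 15/5/10/10/10/15/35% gives 450/150/300/300/300/450/1050.

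Row maxima: 450 + 450 + 300 + 450 + 450 + 750 + 1050 = 3,900. Table 3 and the protocol's Table 1 reproduce exactly. Any mislabelling of the rows in Table 2 therefore passes unchanged into the quotas.

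**2. Set the two lists side by side.**

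| Row | Section 1.5 | Tables 1, 2, 3, 5 | Final count |
|---|---|---|---|
| 1 | 1-2 | 1-4 | 450 |
| 2 | 2-6 | 5-9 | 450 |
| 3 | 6-12 | 10-14 | 300 |
| 4 | 12-19 | 15-19 | 450 |
| 5 | 19-31 | 19-31 | 450 |
| 6 | 31-40 | 31-40 | 750 |
| 7 | 40-65 | 40-65 | 1050 |

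**3. Size if the section 1.5 bands were the ones simulated.** Assumptions: section 1.5 limits are half-open (age 1; 2-5; 6-11; 12-18), samples are spread evenly within a band, and counts transfer row by row.

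Samples per single year under section 1.5: 450/1 = 450; 450/4 = 112.5; 300/6 = 50; 450/7 = 64.3.

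Re-binned to the table bands:

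- Ages 1-4: 450 + 3 × 112.5 = 787.5, against 450.
- Ages 5-9: 112.5 + 4 × 50 = 312.5, against 450.
- Ages 10-14: 2 × 50 + 3 × 64.3 = 292.9, against 300.
- Ages 15-18: 4 × 64.3 = 257.1, against 450 for the row labelled 15-19.

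These four sum to 1,650, as do the four table rows, so the total is unchanged.

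In the other direction, samples per year under Table 1 are 450/4 = 112.5 at ages 1-4, 450/5 = 90 at ages 5-9 and 300/5 = 60 at ages 10-14:

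- Ages 6-11: 4 × 90 + 2 × 60 = 480, against 300 under section 1.5.
- Ages 12-18: 3 × 60 + 4 × 90 = 540 if the 15-19 band covers five years, or 3 × 60 + 450 = 630 if age 19 is counted in 19-31, against 450 under section 1.5.

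**4. Check whether the printed bands partition the ages.** With inclusive limits, ages 19, 31 and 40 each belong to two bands. With half-open limits nothing overlaps, but ages 4, 9 and 14 belong to no band. No single convention works. The dummy table in Appendix 3 puts 19 in 15-19 and starts the next band at 20, so at age 19 two conventions collide.

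**The case against.** A reader might infer that the allocation is not the optimum, or that shares found for one set of ages were applied to another. The documents do not support that. Table 2 itself labels the optimal proportions with the 1-4, 5-9, 10-14 and 15-19 bands, so an outdated list in section 1.5 explains the mismatch equally well. Table 5 does not decide it, because the text gives no projected prevalence by band against which to test its figures.

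Other points on the plan's side also stand:

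- The final allocation is openly a row-wise maximum over three pathogens. Its shares (11.5/11.5/7.7/11.5/11.5/19.2/26.9%) match no column of Table 2 and would not be a single-pathogen optimum even with matching bands.
- The precision the study relies on is in Appendix 5 Tables 4 and 5, both stated for the final allocation, and Table 5 prints the same bands and counts as the quotas. The mismatch does not by itself invalidate those figures.
- Overall precision is not very sensitive to age structure: Table S1 gives 1.02% to 1.20% for measles at 3,000 samples across three structures.
- The shared limits at 31 and 40 appear in both lists, so they say nothing about whether the optimum was misapplied, and they may be half-open notation.
- Laboratories are to receive numbers by single year of age, and each sample's age in years is transferred. The bands may therefore not be the literal laboratory quota, and analysis groups can be formed whatever the recruitment bands.
- The eight groups in section 1.4 fit neither list, but they belong to a different comparison and may be a slip. They are weak evidence.

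The contradiction between section 1.5 and the tables remains, as does the undefined quota at age 19. Numbers by single year still have to be derived from Table 1, which does not say how to treat that age.

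**Conclusion.** The point holds as a contradiction in the basis of the recruitment quota. Table 1 cannot be shown to derive from the optimisation described in section 1.5, because the four youngest bands differ and no conversion is given. As a separate fault, Table 1 mixes two labelling conventions, which is a definite ambiguity at age 19 and a possible one at 31 and 40.

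The size is conditional. If the section 1.5 bands were simulated, and under the half-open, even-spread and row-by-row assumptions, the final counts imply about 788 samples at ages 1-4 instead of 450, and 300 at ages 6-11 instead of about 480. If the table bands were simulated, no count changes and only the text is wrong. In both cases the total of 3,900 and the three adult rows are untouched by the mismatch. No effect on precision has been calculated, and none is claimed.

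**What to change.** 1. Establish from the simulation code which age bands were used in the search.
2. Print one mutually exclusive set in Appendix 5 sections 1.4 and 1.5, in the protocol's Table 1 and in Appendix 5 Tables 2, 3 and 5, before labels are issued. One example is 1-4, 5-9, 10-14, 15-19, 20-30, 31-40 and 41-65, whose cut after 40 matches the 11-40 analysis group for measles. Correct or explain the eight groups in section 1.4.
3. Only if the section 1.5 bands were the ones simulated, rerun the search and the precision tables on the printed bands at the same total of 3,900, and restate the counts and the precision.

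The cost is a text and table correction, or at most a rerun of existing simulation code, after which the stated precision may change slightly. No additional samples are required.

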2.1. Allocation of samples for measles

We conducted the analysis at the national level. As described in the previous section, we estimated the seroprevalence of individuals in 2025 thanks to a multicohort model based on 2013 serological data (Figure 3).

[figure not shown]

Figure 3. Estimated seroprevalence profiles in 2025 in Belgium (measles). Estimates were derived from the multicohort model that incorporates vaccination coverage, waning of vaccine-induced immunity, and baseline seroprevalence from 2013.

Figure 4 presents the expected overall seroprevalence and associated uncertainty (95% simulation interval) for each region across increasing sample sizes (1000, 2000, 3000, 4500 individuals), under three age-based sampling structures: survey-based (sero), population-based (pop), and uniform (unif) sampling structures. The differences between sampling structures were generally modest for overall seroprevalence, although the population-based structure often yielded slightly better precision due to the higher number of samples among young people.

[figure not shown]

Figure 4. Measles serological data: mean, median and 95% confidence interval for the overall seroprevalence over 500 simulations as a function of the total number of sampled individuals (N).

2.2. Allocation of samples for Hepatitis B

We estimated age-specific hepatitis B seroprevalence using data from the 1993 Belgian serological survey. Figure S4 shows the observed seroprevalence along with smoothed estimates obtained from a generalized additive model (GAM) using a complementary log-log link and a smooth function of age. These estimates were used as input to simulate the precision of overall seroprevalence under varying sample sizes and sampling structures.

Figure 6 presents the resulting estimates of overall seroprevalence (mean, median, and 95% confidence intervals) based on 500 simulations across four total sample sizes (1,000 to 9,000) and three age-based sampling strategies: survey-based, population-based, and uniform. Only marginal differences are observed between the three sampling strategies. For a sample size of 1,000, the population-based design yielded the best precision, whereas for 3,000 samples, the survey-based design performed slightly better. A summary of the precision values obtained for each scenario is available in Supplementary Table S2.

[figure not shown]

Figure 6. Hepatitis B serological data: mean, median and 95% confidence interval for the overall seroprevalence over 500 simulations as a function of the total number of sampled individuals.

2.3. Allocation of samples for CMV

We estimated age-specific cytomegalovirus (CMV) seroprevalence using data from the 2011 Belgian serological survey. Figure S5 displays the observed seroprevalence and the fitted estimates obtained from a GAM. These model-based estimates were used to simulate the precision of overall CMV seroprevalence under various sample sizes and sampling strategies.

Figure 9 summarizes the results from 500 simulations, showing the mean, median, and 95% confidence intervals of overall seroprevalence across four total sample sizes (1,000 to 9,000) and three sampling structures (survey-based, population-based, and uniform). The three sampling designs yielded very similar results. The population-based structure showed slightly better precision at 1,000 samples, whereas the survey-based design performed best at 3,000 samples.

Based on these results, we recommend allocating at least 1,000 samples per region for CMV, corresponding to 3,000 samples nationally. With this total sample size, the estimated precision for the overall CMV seroprevalence at the national level ranges between $\pm 2.8\%$ and $\pm 3.4\%$, depending on the sampling strategy. Although this is sufficient for generating national estimates, it does not provide acceptable precision for regional-level estimates. To ensure adequate precision at the regional scale (e.g., $\pm 2\%$), a higher number of samples per region would be required. Detailed precision values for each sample size and sampling design are provided in Supplementary Table S3.

[figure not shown]

Figure 9. CMV serological data: mean, median and 95% confidence interval for the overall seroprevalence over 500 simulations as a function of the total number of sampled individuals.

3. Conclusions

We recommend allocating 3,900 samples nationally, corresponding to approximately 1,300 samples per region (Flanders, Brussels, and Wallonia), to ensure acceptable precision (below $\pm 2\%$) for estimating the overall seroprevalence of measles, hepatitis B, and CMV at the regional level.

An optimisation algorithm was used to test multiple age-based sampling distributions and identify the most efficient allocation for each pathogen. Table 2 summarises the optimal proportions of samples by age group, which differ slightly across pathogens. These proportions were then translated into absolute sample counts (Table 3), assuming 3,000 samples per pathogen at the national level.

To ensure sufficient precision for all pathogens, we selected the maximum number of samples per age group across the three pathogens as the final recommendation. This results in a total of 3,900 samples nationally, which we divide equally across the three regions, yielding 1,300 samples per region.

Table 4 reports the expected precision of the overall seroprevalence estimates under this allocation. At the national level (3,900 samples per pathogen), the expected precision is 0.82% for measles, 0.85% for hepatitis B, and 1.69% for CMV. At the regional level (1,300 samples per region), expected precision decreases slightly to 1.69% for measles, 1.45% for hepatitis B, and 2.64% for CMV, still within acceptable bounds.

Age group	Measles	НерВ	CMV
1-4yo	5%	5%	15%
5-9yo	15%	15%	5%
10-14yo	5%	10%	10%
15-19yo	15%	5%	10%
19-31yo	15%	10%	10%
31-40yo	20%	25%	15%
40-65yo	25%	30%	35%
Precision	0,88%	0,74%	1,52%

Table 2. Optimal proportion of samples per age group for measles, hepatitis B, and CMV based on national-level simulations.

	Measles	НерВ	CMV	National	Regional
1-4yo	150	150	450	450	150
5-9yo	450	450	150	450	150
10-14yo	150	300	300	300	100
15-19yo	450	150	300	450	150
19-31yo	450	300	300	450	150
31-40yo	600	750	450	750	250
40-65yo	750	900	1050	1050	350
Total	3000	3000	3000	3900	1300

Table 3. Absolute number of samples per age group, assuming 3,000 samples per pathogen. The final allocation (bold values) corresponds to the highest required count across pathogens, resulting in a total of 3,900 samples nationally (or approximately 1,300 per region).

	Measles	НерВ	CMV
National	0,82%	0,85%	1,69%
Regional	1,69%	1,45%	2,64%

Table 4. Expected precision (half-width of the 95% simulation-based confidence interval) for overall seroprevalence estimates under the final allocation. National precision is based on 3,900 samples; regional precision is based on 1,300 samples per region.

Precision by age - national allocation

_	.=			
Age group	Allocation	Measles	НерВ	CMV
1-4yo	450	2,25%	0,50%	4,23%
5-9yo	450	2,61%	0,53%	3,25%
10-14yo	300	1,76%	0,63%	3,50%
15-19yo	450	1,95%	0,73%	3,14%
19-31yo	450	2,88%	1,20%	2,94%
31-40yo	750	2,40%	1,51%	2,78%
40-65vo	1050	1,25%	1.42%	3.02%

Table 5. Expected precision (half-width of the 95% simulation-based confidence interval) for prevalence estimates of each age group under the final allocation.

4. References of Appendix 5

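### Appendix 5 concludes that 1,300 samples per region give precision below ±2% for CMV, but its Table 4 gives 2.64%, and section 2.3 misstates the national CMV range at 3,000 samples

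*Protocol*

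**What the plan says.** Appendix 5, section 3 reads: "We recommend allocating 3,900 samples nationally, corresponding to approximately 1,300 samples per region". The stated purpose is a precision below ±2% "for estimating the overall seroprevalence of measles, hepatitis B, and CMV at the regional level". Section 1.4 fixes the measure: "precision was defined as half of the width of the 95% simulation-based confidence interval across the 500 replicates".

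The same section then reports Table 4. Nationally, at 3,900 samples, "the expected precision is 0.82% for measles, 0.85% for hepatitis B, and 1.69% for CMV". Regionally, at 1,300 samples, "expected precision decreases slightly to 1.69% for measles, 1.45% for hepatitis B, and 2.64% for CMV, still within acceptable bounds".

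Section 2.3 recommends at least 1,000 CMV samples per region, 3,000 in all. With that total, it says, "the estimated precision for the overall CMV seroprevalence at the national level ranges between" ±2.8% and ±3.4%, which it judges enough for national but not for regional estimates. It refers to Table S3 for the detail. On sampling structure it says that population-based sampling was slightly better at 1,000 samples, "whereas the survey-based design performed best at 3,000 samples". Section 2.2 likewise says that the survey-based design did slightly better at 3,000 for hepatitis B, and refers to Table S2.

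The Sample size section of the main protocol claims precision below 2% for all three pathogens only for overall national estimates. It calls similar absolute numbers in the three regions unfeasible and accepts wider intervals in Brussels.

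**The concern.** The conclusion of the sample-size appendix names a bound, and the table that supports it exceeds that bound for one of the three pathogens. The text then treats 2.64% as acceptable shortly after defining acceptable as below ±2%.

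In section 2.3 the range given for the national sample is not the one in the table it cites. Taken literally, it says that a national half-width of up to 3.4% is enough, although the main protocol aims for ±2%.

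The serum bank is to serve several pathogens over five years, chosen by the steering committee, and CMV is on the candidate list in Appendix 1. A committee relying on the conclusion could expect ±2% in each region for a marker with mid-range prevalence. The appendix's own figures do not offer that.

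**Working it through.** **Inputs.** Regional and national half-widths come from Table 4. CMV half-widths by sample size and structure, and overall CMV prevalence of about 0.348, come from Table S3. Hepatitis B half-widths come from Table S2. The number of replicates, 500, comes from section 1.4.

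**1. Regional CMV claim against Table 4.** At 1,300 per region: measles 1.69%, hepatitis B 1.45%, CMV 2.64%. Only CMV misses 2%, with 2.64 / 2.00 = 1.32.

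**2. Is Table 4 credible for CMV?** The simulation cannot be rerun, because the CMV age profile appears only in a figure that is not shown. A simple binomial half-width is 1.96 × √(p(1−p)/n), with p(1−p) = 0.348 × 0.652 = 0.2269:
- n = 1,000: 2.95%
- n = 1,300: 2.59%
- n = 3,000: 1.70%

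Scaling every CMV row of Table S3 to 1,300 by √(n/1,300) gives 2.34% (uniform, from 3,000) to 3.16% (survey-based, from 6,000). No variant is below 2%, and 2.64% lies inside the range.

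**3. Size of the shortfall.** Scaling from Table 4, a CMV half-width of 2% needs 1,300 × (2.64/2)² = 1,300 × 1.7424, or about 2,266 samples in a region. The binomial formula gives 2,180. This only gauges the gap and is not a proposed sample size.

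**4. Section 2.3 range against Table S3.**

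| CMV samples | Survey-based | Population-based | Uniform |
|---|---|---|---|
| 1,000 | 3.476% | 3.053% | 2.886% |
| 3,000 | 2.002% | 1.585% | 1.540% |

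The stated ±2.8% to ±3.4% at 3,000 should be about 1.54% to 2.00%. It is too wide by 2.8/1.54 = 1.8 at the lower end and 3.4/2.00 = 1.7 at the upper end. The 1,000-sample rows run from 2.886% to 3.476%, which give 2.8 and 3.4 if truncated and 2.9 and 3.5 if rounded. Table 2 also points to the lower values: 1.52% for CMV under the optimised allocation, which Table 3 sets at 3,000 samples.

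**5. Ranking of structures.** Assume near-normal estimates. A half-width from the empirical 2.5% and 97.5% points of 500 replicates then has a relative Monte Carlo standard error of about 4% (about 3% if based on the standard deviation). A comparison of two structures has about 4.5% to 6%.
- CMV at 3,000, survey-based against uniform: 2.002/1.540 = 1.30; against population-based: 2.002/1.585 = 1.26. Both are far beyond noise, so survey-based is clearly the least precise. It has the widest half-width at all four sizes in Table S3.
- CMV, uniform against population-based: 1.585/1.540 = 1.03 at 3,000 and 3.053/2.886 = 1.06 at 1,000. Both are within noise.
- Hepatitis B at 3,000, survey-based 0.785% against population-based 0.748%: ratio 1.05, in the opposite direction to section 2.2 and within noise.

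**The case against.** The strongest reply is that nothing in the design rests on these sentences, and most of it stands.

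- A reader might infer that the total of 3,900 loses its justification. It does not. Section 3 takes the largest count per age group across the three pathogens, and the Table 3 maxima give 450 + 450 + 300 + 450 + 450 + 750 + 1,050 = 3,900. The misquoted range does not enter that sum.
- A reader might infer that the wrong age structure was adopted. None of the three compared structures was; the allocation comes from the optimisation in section 1.5.
- A reader might infer that the protocol as a whole promises ±2% by region. The main Sample size section limits that figure to national estimates, which Table 4 supports (0.82%, 0.85% and 1.69%).
- The 2.64% is disclosed directly after the claim, and section 2.3 itself warns that ±2% by region needs more than 1,000 samples per region.
- Measles is the first priority and meets the bound at 1,300. CMV is only a candidate pathogen.
- It would be tempting to name uniform sampling as best for CMV, or population-based as best for hepatitis B. Those gaps of 3% to 6% are within simulation noise.

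These points limit the consequence. They do not make the regional CMV statement or the section 2.3 range correct.

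**Conclusion.** The regional conclusion is wrong as written for CMV: 2.64% against a stated bound of 2%, about a third wider. It is right for measles and hepatitis B, provided a region reaches 1,300 samples. The main protocol does not expect equal numbers to be feasible in Brussels, so for any given pathogen precision there would be worse than Table 4 shows.

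The national CMV range in section 2.3 is too wide by a factor of about 1.7 to 1.8. That it was taken from the 1,000-sample rows is a close-fitting inference, not something the documents state. With the right rows the section's own judgement makes sense: about ±2% or better nationally, and not adequate for a region of 1,000.

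The statement that survey-based sampling was best at 3,000 is contradicted for CMV and unsupported for hepatitis B.

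The documents support a correction to stated precision, not a finding that the sample size or allocation is unsound. The check relies on the tabulated values, square-root scaling and a simple binomial approximation. The noise estimate assumes near-normal simulated estimates.

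**What to change.** All changes are within Appendix 5.

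- Section 3: state that at 1,300 samples in a region the expected half-width is below ±2% for measles (1.69%) and hepatitis B (1.45%) and about ±2.6% for CMV. Add that this holds only where 1,300 are obtained, and refer to the main text on Brussels. Remove the description of 2.64% as acceptable, or state the wider bound that is meant for CMV.
- Section 2.3: give national CMV precision at 3,000 samples as about ±1.5% to ±2.0%, and the precision for one region of 1,000 as about ±2.9% to ±3.5%.
- Sections 2.2 and 2.3: delete the statements that survey-based sampling did best at 3,000. For CMV, say that it was clearly the least precise; say that the other differences are within simulation noise.

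The cost is text only, with no new simulation. The one practical effect is that the stated regional figure for CMV becomes less favourable.
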